8.8 Week 22 (post-randomisation)

The following will be done in addition to the 6 weekly assessments described above

- Radiological assessment of response using same modality as baseline
 - If progressive disease is identified at radiological review, ensure the Trials Unit are informed immediately using the Progression Notification Form (see section 3.2).
- Document decision about further TACE to be performed. Prior to subsequent TACE, the trial entry criteria should be met. Scans may be done more frequently if clinically indicated

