4 ELIGIBILITY AND WITHDRAWAL OF PATIENTS

4.1 Inclusion Criteria

- Histological or cytological diagnosis or meet the AASLD criteria (Appendix 1) for diagnosis of HCC and at least one uni-dimensional lesion measurable according to the RECIST criteria by CT-scan or MRI (Appendix 2).
- Not a candidate for surgical resection or liver transplant
- Aged ≥18 years and estimated life expectancy >3 months
- ECOG performance status ≤1 (Appendix 3)
- Adequate haematological function Hb ≥9g/L, absolute neutrophil count ≥1.5x10⁹/L, platelet count ≥60x10⁹/L
- Bilirubin ≤50 µmol/L, AST and ALT ≤5 x ULN, ALP <4 x ULN
- Adequate renal function; Creatinine ≤1.5 x ULN
- INR ≤1.5
- Amylase <2 x ULN
- Child-Pugh A (score ≤6) (Appendix 4)
- Left Ventricular Ejection Fraction ≥45%
- Women of child-bearing potential should have a negative pregnancy test prior to study entry. Both men and women must be using an adequate contraception method, which must be continued for 3 months after completion of treatment
- Written informed consent

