4.2 Exclusion Criteria

- Extrahepatic metastasis
- Prior embolisation, systemic or radiation therapy for HCC
- Any contraindications for hepatic embolisation procedures including portosystemic shunt, hepatofugal blood flow, known severe atheromatosis
- Investigational therapy or major surgery within 4 weeks of trial entry
- Any ablative therapy (RFA or PEI) for HCC (this should not exclude patients if target lesion(s) have not been treated and occurred >6 weeks prior study entry)
- History of bleeding within the past 4 weeks
- Child-Pugh cirrhosis C or B (score ≥7)
- Hepatic encephalopathy
- Ascites refractory to diuretic therapy
- Documented occlusion of the hepatic artery or main portal vein
- Hypersensitivity to intravenous contrast agents
- Active clinically serious infection > Grade 2 NCI-CTC version 4 (Appendix 5)
- Pregnant or lactating women
- Known history of HIV infection
- History of second malignancy except those treated with curative intent more than three years preciously without relapse and non-melanotic skin cancer or cervical carcinoma in situ
- Evidence of severe or uncontrolled systemic diseases, cardiac arrhythmias (requiring anti-arrhythmic therapy or pace maker), uncontrolled hypertension, congestive cardiac failure >NYHA class 2 (see Appendix 6), MI within 6 months, prolonged QT/QTc >450ms, or laboratory finding that in the view of the Investigator makes it undesirable for the patient to participate in the trial
- Psychiatric or other disorder likely to impact on informed consent
- Patient is unable and/or unwilling to comply with treatment and study instructions
- Patient unable to swallow oral medications

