and diastolic BP < 110 mm	Begin anti-hypertensive therapy and continue sorafenib
Hg	

^b if no recovery after 30 days discontinue study treatment

Grade 2	Discontinue treatment ^a until symptoms resolve and diastolic
symptomatic/persistent	BP returns to ≤100 mm Hg. Treat subject with anti-
OR	hypertensives and restart at reduced level ^b
Diastolic BP ≥110 mm Hg	If diastolic BP not controlled to ≤100 mm Hg on therapy,
OR	reduce treatment by another dose level and monitor BP
Grade 3	closely ^c
Grade 4 life-threatening	Discontinue treatment

Monitoring of ECG Readings

ECGs will be carried out according to the schedule in Appendix 12. Sorafenib should be discontinued if QT/QTc increases over 500ms or increases to 60ms above the baseline reading.

Please note that specific criteria are not completely identical to NCI-CTCAE V4 criteria

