APPENDIX 11: EXPECTED ADVERSE EVENTS

Very Common or Common Events	TACE using DC Bead [®] loaded with Doxorubicin	Sorafenib
Haematological Lymphopenia		
Leucopenia	√ ·	V
Neutropenia	V	V
Thrombocytopenia	V	V
Anaemia	V	V
Gastrointestinal Anorexia	V	$\sqrt{}$
Weight decreased		V
Increased amylase		V
Increased lipase		V
Dyspepsia		\checkmark
Dysphagia		\checkmark
Gastroesophageal reflux disease		√
	,	,
Diarrhoea	V	V
Nausea	V	V
Vomiting	V	V
Constipation		V
Stomach aches	$\sqrt{}$	
Perforation		\checkmark
Stomatitis	V	$\sqrt{}$
Renal Nephrotoxicity	$\sqrt{}$	
Renal Failure		V
Proteinuria		V
Respiratory Rhinorrhoea		V
Dysphonia		\checkmark
Hepatic Liver dysfunction/failure	V	
Abnormal liver transaminases	√	
Transient increase in transaminases		V
Infection Liver abscess	√	
Infections		√
Folliculitis		
Endocrine Hypothyroidism		V
Neurotoxicity Peripheral neuropathy	V	V
Dysguesia		V
Ear disorders Tinnitus		\checkmark

Ocula	r toxicity	V	
Cardiac Disorders Congestive hea	rt failure		\checkmark
Myocardial ischaemia and ir	nfarction		V
Cardi	otoxicity	\checkmark	
Skin disorders	Dry skin		$\sqrt{}$
	Rash	\checkmark	V
,	Alopecia	√	V
Hand foot skin	reaction		V
E	rythema		√
	Pruritus		√
Keratocanthoma/squamous cell skir	cancer		√
Dermatatis ex	foliative		√
	Acne		√
Skin desqu	amation		√
Hyperk	eratosis		√
Musculoskeletal	Myalgia		√
Muscle	spasms		√
	rthralgia	,	V
Other Raised temp		V	V
Haem	orrhage	V	V
	Pain	√	V
	rtension		V
Hypophosph	ataemia		√
Нуросаса	Icaemia		√
Hypok	alaemia		√
Hypona	atraemia		V
Dep	oression		,
	Fatigue		V
I	Flushing		V
Erectile dys	function		V
ļ ,	Asthenia		V
Influenza-lik	e illness		V

Uncommon/Rare Events	TACE using DC Bead [®] loaded with Doxorubicin	Sorafenib
Hypersensitivity reactions/anaphylaxis		√
Angioedema		√
Hyperthyroidism		√
Dehydration		√
Reversible posterior leukoencephalopathy		√
QT prolongation		V
Hypertensive crisis		√
Interstitial lung disease events		√
Pancreatitis		√
Gastritis		√
Gastrointestinal perforations		√
Increase in bilirubin and jaundice		√
Drug induced hepatitis		V
Cholecystitis/cholangitis		V
Eczema		V
Erythema multiforme		\checkmark
Radiation recall dermatitis		\checkmark
Stevens-Johnson syndrome		\checkmark
Toxic epidermal necrolysis		\checkmark
Leucocytoclastic vasculitis		\checkmark
Rhabdomyolysis		√
Nephrotic syndrome		\checkmark
Gynaecomastia		√
Transient increase in blood alkaline phosphatase		√
Abnormal INR/prothrombin level		\checkmark

Unknown Frequency	
Encephalopathy	V

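### From week 22, repeat TACE depends on entry criteria that no embolised patient can meet, and the LVEF rule after six procedures is inverted

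*Protocol*

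**What the plan says.** Section 8.8 (week 22) sets this condition for a further procedure: "Prior to subsequent TACE, the trial entry criteria should be met". Section 8.9 (week 34 and 12-weekly thereafter) repeats it word for word. Neither gives a list, a cross-reference or an exception. Section 6, headed Trial Entry, deals with randomisation, so the criteria can only be those of sections 4.1 and 4.2. They include:

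- 4.1: "Left Ventricular Ejection Fraction ≥45" per cent, and "Amylase <2 x ULN".
- 4.2: "Prior embolisation, systemic or radiation therapy for HCC", "Documented occlusion of the hepatic artery or main portal vein", and "prolonged QT/QTc >450ms".

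Two other sections govern the same decision. Section 8.6 (week 10) requires the inclusion levels for haematology, renal function and liver function, and nothing else. Section 7.2 says that a tumour not completely devascularised should be retreated unless technical or patient factors stand in the way. It does not mention entry criteria.

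Section 7.2 also has an LVEF rule that starts after six procedures. Its first sentence permits further DC Bead TACE only if LVEF is below 45% on repeat assessment. Its second prescribes bland embolisation with unloaded beads if LVEF is below 45%.

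**The concern.** Sections 8.8 and 8.9 decide whether a patient receives another invasive procedure. Followed as written, they never allow one. Sites will presumably set aside the prior-embolisation exclusion, but they then have to decide for themselves which other criteria still apply, with 8.6 and 7.2 pointing to different tests. The trial presents a common TACE protocol as a design feature (section 1.4), so an undefined retreatment threshold works against its own aim.

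The LVEF sentence is a safety matter in its own right. Appendix 11 lists cardiotoxicity under doxorubicin-loaded TACE. A limit meant to protect patients with reduced cardiac function instead reserves further loaded beads for them.

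**Working it through.** The retreatment condition involves no statistical calculation; the check sets the sections side by side.

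**1. Can the condition be met?** A candidate for repeat TACE has by definition been embolised at least once, and 4.2 excludes prior embolisation. So no candidate meets all entry criteria, in either arm.

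**2. Do the rules agree?**

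| Section | When | Test for repeat TACE |
|---|---|---|
| 7.2 | general | residual vascularity; no technical or patient reason against |
| 8.6 | week 10 | haematological, renal and liver function at inclusion levels |
| 8.8, 8.9 | week 22 onward | all entry criteria, unqualified |

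The test widens between week 10 and week 22 without explanation. Section 7.6 leaves further treatment to the clinician and does not define the condition.

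**3. Can it be checked?** Appendix 12 marks LVEF and amylase at screening only, and the biochemistry panel in its first footnote omits amylase. ECG is repeated at the 6-weekly visits. From week 22, two of the entry criteria therefore have no scheduled measurement.

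**4. The LVEF rule in 7.2, after six procedures.**

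| LVEF | First sentence | Second sentence |
|---|---|---|
| below 45% | loaded beads allowed | bland embolisation |
| 45% or more | loaded beads not allowed | no instruction |

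Below 45% the two sentences conflict; at 45% or more the patient has no option. With the sign in the first sentence reversed, both rows make sense and match 4.1. Added to the entry requirement of at least 45%, the uncorrected sentence leaves nobody eligible for loaded beads.

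**5. When would the LVEF rule apply?** Take decisions at weeks 10, 22, 34, 46, 58 and 70.

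- Single sessions throughout: the first TACE is procedure 1, weeks 10 to 58 give procedures 2 to 6, and the seventh falls at week 70.
- First TACE split by lobe: procedures 1 and 2, weeks 10 to 46 give 3 to 6, and the seventh falls at week 58.
- Every treatment split, which Appendix 7 does not rule out: two procedures each at the first TACE, week 10 and week 22 make six, and the seventh falls at about week 34.

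The timing thus depends on how often treatment is split, and the protocol does not give that frequency.

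**The case against.** Several points on the other side stand.

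- The condition says should, which leaves room for judgement, and a sensible site would not apply the prior-embolisation exclusion. This softens the literal reading but does not supply the missing subset.
- A stricter test for later procedures may have been intended. If so, it still has to be named.
- Bland embolisation carries no chemotherapy, so the second LVEF sentence in 7.2 can be read as a special rule outside a condition on TACE. That is fair; the inverted first sentence remains.
- After trial closure 7.2 allows TACE by local NHS practice, which narrows the scope to DC Bead procedures before closure.

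A reader might go further and infer that sorafenib could lower the 12-month TACE count by making patients fail the condition. Appendix 11 does list "Increased amylase" and QT prolongation under sorafenib and not under TACE. The documents do not support that inference:

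- Amylase is not measured after screening, so a raised value would surface only through an unscheduled test.
- QT prolongation is listed as uncommon or rare.
- Randomisation is minimised by centre, which largely balances differing site practice between arms. Treatment is blinded until progression or closure to recruitment, decisions about further TACE are documented, and the count is reported only descriptively (13.2).
- The organ-function test in 8.6 could also be failed through sorafenib, since Appendix 11 lists neutropenia, thrombocytopenia, renal failure and transaminase rises under it. The argument therefore does not separate the present wording from the repair.

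Nor is there a QTc contradiction. Section 7.3 says "Sorafenib should be discontinued if QT/QTc increases over 500ms or increases to 60ms above the baseline reading", while the entry limit is 450 ms. One governs stopping a drug and the other, if it applies, governs repeating a procedure; the two limits may differ.

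Progression-free shares do not size the effect either. With the design medians of 8.9 and 12.4 months and exponential PFS, week 22 (5.06 months) gives 0.5^(5.06/8.9) = 67% and 0.5^(5.06/12.4) = 75%. Those are patients still on schedule, not patients with residual vascularity being considered for TACE.

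**Conclusion.** The point holds as a defect in two treatment rules. The week 22 condition cannot be satisfied as written, disagrees with 8.6 and 7.2, and cannot be fully checked with the planned assessments. The LVEF sentence in 7.2 is inverted, as the sentence after it and the inclusion criterion both show. These conclusions rest on the text alone, on the assumption that the criteria meant are those of 4.1 and 4.2.

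The likely consequences are retreatment decisions that differ between sites, retreatment wrongly withheld where a site follows the text, and a cardiac rule that points the wrong way. How many patients would be affected cannot be derived from the protocol. Bias in the TACE count is not shown, and neither is any effect on PFS, power or the error rate. The correction should be made because the rules are operative and the repair is cheap.

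**What to change.** In 8.8 and 8.9, replace the condition with:

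1. The organ-function requirement of 8.6.
2. A closed list of current contraindications drawn from 4.2: occlusion of the hepatic artery or main portal vein, hepatofugal flow or portosystemic shunt, active serious infection, and any others the investigators want, such as encephalopathy or refractory ascites.
3. A statement that prior study TACE and study drug do not count as exclusions.

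In 7.2, change the loaded-bead sentence to LVEF of 45% or more, keep bland embolisation below 45%, and let 7.2 alone govern LVEF at repeat procedures. If amylase or QTc is meant to restrict repeat TACE, name the limit in 8.8 and 8.9 and, for amylase, add the test to Appendix 12.

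The cost is protocol wording in 8.8, 8.9 and 7.2. No procedure is added beyond the repeat LVEF assessment that 7.2 already calls for, unless the investigators choose a further criterion that needs a new test.

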8.9 Week 34 (post-randomisation) and 12 weekly thereafter until progression

The following will be done in addition to the 6 weekly assessments described above

• Document decision about further TACE to be performed. Prior to subsequent TACE, the trial entry criteria should be met.

9 SAFETY ASSESSMENTS

9.1 Definition of Adverse Event

An Adverse Event (AE) is defined as any untoward medical occurrence in a patient or clinical trial patient administered study treatment (i.e. TACE or sorafenib or matching placebo) and which does not necessarily have a causal relationship with the treatment received.

Comment: An AE can therefore be any unfavourable and unintended sign (including abnormal laboratory findings), symptom or disease temporally associated with the use of the study treatment, whether or not it is considered related to the study treatment.

9.2 Definition of Adverse Reaction

An Adverse Reaction (AR) is defined as all untoward and unintended responses to study treatment related to any dose administered.

Comment: An AE judged by either the reporting Investigator or Sponsor as being possibly related, probably related, or definitely related to study therapy will qualify as an AR.

9.3 Definition of Unexpected Adverse Reaction

An Unexpected Adverse Reaction (UAR) is defined as an AR, the nature or severity of which is not consistent with the applicable product information.

Comment: When the outcome of an AR is not consistent with the applicable product information, the AR should be considered unexpected.

If the Investigator suspects that the disease has progressed faster due to the administration of the IMP, then they will report this as an unexpected adverse event to the Trials office.

9.4 Definition of Serious Adverse Event

An SAE is defined as any untoward medical occurrence or effect that at any dose:

- Results in death
- Is life-threatening*
- Requires inpatient hospitalisation** or prolongation of existing hospitalisation
- Results in persistent or significant disability or incapacity
- Is a congenital anomaly/birth defect
- Or is otherwise considered medically significant by the Investigator (i.e. an event that jeopardizes the patient or may require intervention to prevent one of the other outcomes listed above)

- * Life threatening in the definition of an SAE refers to an event in which the patient was at risk of death at the time of the event; it does not refer to an event that hypothetically might have caused death if it were more severe.
- ** Hospitalisation is defined as an unplanned, overnight, formal inpatient admission, even if the hospitalisation is a precautionary measure for continued observation. Thus hospitalisation for protocol treatment (e.g. line insertion), elective procedures (unless brought forward because of worsening symptoms) or for social reasons (e.g. respite care) are not regarded as an SAE

Comment: The term severe is often used to describe the intensity (severity) of a specific event. This is not the same as serious, which is based on patients/event outcome or action criteria.

9.5 Definition of Serious Adverse Reaction (SAR)

A Serious Adverse Reaction (SAR) is a SAE judged by either the reporting Investigator or Sponsor as being possibly related, probably related, or definitely related to study therapy.

9.6 Definition of Suspected Unexpected SAR (SUSAR)

A Suspected Unexpected Serious Adverse Reaction (SUSAR) is defined as a SAR that is unexpected i.e. the nature, seriousness, severity (i.e. grade) or outcome of the event is not consistent with the applicable product information.

9.7 List of Expected Adverse Reactions

For a list of all expected adverse reactions please refer to the Summary of Product Characteristics (SmPC) for sorafenib and for the TACE procedure, refer to both the related SmPC for doxorubicin and the list of AEs for the embolisation procedure given in Appendix 11.

9.8 Assessment of Adverse Events

For all AEs, the Investigator will determine the grade (i.e. severity), seriousness and causality (i.e. relationship to study therapy) as described below. When assessing SAEs the Investigator must assume that the patient received the active IMP (i.e. sorafenib).

• Grade (i.e. severity)

All events should be graded according to the NCI CTCAE Toxicity Criteria (Version 4)

For events not listed in the toxicity table, severity should be recorded as:

Mild	Does not interfere with patient's usual functioning
Moderate	Interferes to some extent with patient's usual functioning
Severe	Interferes significantly with patient's usual functioning

• Causality (i.e. Relationship to Study therapy)

Relationship to study therapy will be assessed using the following definitions:

Unrelated	There is no evidence of any causal relationship
Unlikely to be related	There is little evidence to suggest there is a causal relationship (e.g. the event did not occur within a reasonable time after administration of the trial medication). There is another reasonable explanation for the event (e.g. the patient's clinical condition, other concomitant treatments).
Possibly related	There is some evidence to suggest a causal relationship (e.g. the event occurred within a reasonable time after administration of the trial medication). However, the influence of other factors may have contributed to the event (e.g. the patient's clinical condition, other concomitant events).
Probably related	There is evidence to suggest a causal relationship, and the influence of other factors is unlikely.
Definitely related	There is clear evidence to suggest a causal relationship, and other possible contributing factors can be ruled out.

9.9 Independent Assessment of Causality and Expectedness

Seriousness and causality of all reported SAEs will be determined independently by the TACE-2 Clinical Coordinator. An SAE judged by the Chief Investigator, or delegated Clinical Coordinator, to have a reasonable causal relationship with the trial medication will be regarded as a SAR (i.e. possibly related, probably related, or definitely related to study therapy). The Clinical Coordinator will also assess all SARs for expectedness. If the event meets the definition of a SAR that is unexpected in nature it will be classified as a SUSAR.

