10.7 Reporting by Sponsor

All unexpected serious adverse reactions will be notified to the sponsor immediately according to the sponsor's SOP. Reporting by the Sponsor or Sponsor's delegated representative is in line with the "Detailed guidance on the collection, verification and presentation of adverse reaction reports arising from clinical trials on medicinal products for human use April 2006".

For the purposes of the trial sorafenib and matching placebo are both classed as Investigational Medicinal Products (IMP), whilst TACE is classed as background treatment and a Non Investigational Medicinal Product (NIMP).

• SUSAR reporting in Member State concerned

The Sponsor, or delegated representative, shall report all individual events which are unexpected and suspected to be related to sorafenib, or matching placebo, or to be linked to an interaction between sorafenib, or matching placebo, and TACE, to the Competent Authority and the Ethics Committee in the Member State concerned as follows:-

If a SUSAR is categorised as a fatal or life threatening SUSAR, a minimal data set of all individual events will be sent within 7 days with detailed follow-up information provided within an additional 8 days.

All other events categorised as SUSARs will be reported within 15 days to the Competent Authority and the Ethics Committee in the concerned Member State.

Regular SUSAR reports to Ethics Committees in other Member states

All SUSARs from other Member States will be periodically reported at least every 6 months as a line listing accompanied by a brief report by the Sponsor/Trials Office highlighting the main points of concern. Those periodic reports shall only include SUSARs reported within the period covered by the report.

Development Safety Update Report (DSUR)

In addition to the above, the sponsor or delegated sponsor's representative shall submit, once a year throughout the clinical trial or on request, a safety report to the Competent Authority and the Ethics Committee of all concerned Member States, taking into account all new available safety information received during the reporting period. The DSUR will

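### Section 9.9 classifies SUSARs on nature alone, narrower than the definitions in 9.3 and 9.6, and does not name the reporting Investigator for SAR status

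*Protocol*

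**What the plan says.** Four parts of the protocol bear on when a serious event becomes a SUSAR.

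- **Section 9.3** defines an unexpected reaction: "An Unexpected Adverse Reaction (UAR) is defined as an AR, the nature or severity of which is not consistent with the applicable product information". Its comment adds outcome: "When the outcome of an AR is not consistent with the applicable product information, the AR should be considered unexpected".
- **Section 9.6** defines a SUSAR as an unexpected SAR, meaning that "the nature, seriousness, severity (i.e. grade) or outcome of the event is not consistent with the applicable product information".
- **Section 9.9** gives the Clinical Coordinator the expectedness assessment and the classification rule: "If the event meets the definition of a SAR that is unexpected in nature it will be classified as a SUSAR".
- **Section 10.7** attaches the deadlines, counted in days, to the category: "If a SUSAR is categorised as a fatal or life threatening SUSAR, a minimal data set of all individual events will be sent within 7". Other SUSARs are due within 15 days.

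On causality, section 9.5 says a SAR "is a SAE judged by either the reporting Investigator or Sponsor as being possibly related, probably related, or definitely related to study therapy". Section 9.2 uses the same either-assessor rule for adverse reactions in general. Section 9.9 sets out whose judgement gives SAR status: "An SAE judged by the Chief Investigator, or delegated Clinical Coordinator, to have a reasonable causal relationship with the trial medication will be regarded as" such. It does not mention the reporting Investigator.

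**The concern.** Section 9.9 is the only section that tells the Coordinator how to get from a SAR to a SUSAR, and its test is narrower than the definition it is meant to apply. The cases that fall between the two are known reactions that turn out worse than the product information describes. In a trial that adds sorafenib to TACE, with toxicity among its secondary objectives, those cases matter.

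The deadlines to the Competent Authority and Ethics Committee run from SUSAR categorisation, so an event not so classified may not start them. The six-monthly line listings in 10.7 are also built from SUSARs.

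The causality wording raises a second, smaller question. Where the site considers an event possibly related and the Coordinator does not, 9.5 gives a clear answer and 9.9 gives none.

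**Working it through.** No arithmetic applies. The check sets the sections side by side.

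**Step 1. Grounds that make a reaction unexpected**

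| Ground | 9.3 | 9.6 | 9.9 |
|---|---|---|---|
| Nature | yes | yes | yes |
| Severity (grade) | yes | yes | not named |
| Outcome | yes (comment) | yes | not named |
| Seriousness | not named | yes | not named |
| Total | 3 | 4 | 1 |

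**Step 2. Does 9.9 import the wider definition by reference?** It does not cite 9.6 or 9.3. The definition it mentions is that of a SAR, which concerns seriousness and causality and not expectedness. The qualifier on nature therefore stands alone as the expectedness test.

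**Step 3. Apply the rules to cases.** Each is a SAR whose causality is agreed.

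- Reaction not in the product information: a SUSAR under both 9.6 and 9.9.
- Listed reaction, grade beyond the product information: a SUSAR under 9.6; under 9.9 read literally, not classified.
- Listed reaction, fatal where the product information does not describe that outcome: a SUSAR under 9.6; under 9.9 read literally, not classified.

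**Step 4. Follow the unclassified event through section 10.** Under 10.2 it reaches the Trials Office within 24 hours as an SAE (apart from the TACE hospitalisations exempted in 10.3) and is passed to the sponsor under the sponsor's SOP. If fatal, 10.4 also requires 24-hour notice to the Trials Office and allows up to 7 days to tell the sponsor. Neither section sends anything to the Competent Authority or Ethics Committee. That is done by 10.7, whose 7- and 15-day limits are written for events categorised as SUSARs.

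**Step 5. Causality.**

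| Section | Whose judgement is named |
|---|---|
| 9.2, 9.5 | reporting Investigator or Sponsor; either suffices |
| 9.8 | Investigator, for every adverse event |
| 9.9 | Chief Investigator or delegated Clinical Coordinator |
| 10.6 | refers to SUSAR classification by Investigator or Clinical Coordinator |

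Take an SAE rated possibly related by the site and unlikely by the Coordinator. Under 9.5 it is a SAR. Section 9.9 says what happens when the central assessor finds a relationship and is silent on what happens when only the site does. No section sets a rule for disagreement.

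**The case against.** The strongest reply is that the definitions in 9.3 and 9.6 remain in force, and that one loosely worded sentence should be read in their light. Section 10.7 supports this: its duty to report covers events that are unexpected and suspected to be related, with no restriction to nature, and it has unexpected serious reactions notified to the sponsor immediately. A sponsor working from 9.6 and 10.7 would still report the event. This has force and limits the point to a risk that arises if 9.9 is applied literally. It does not remove the risk, because 10.7 supplies no expectedness test of its own and 9.9 is where the test is applied.

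A reader might go further in four ways that the protocol does not support.

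- **That such events escape expedited reporting altogether.** They do not: 10.2 and 10.4 bring SAEs and deaths to the Trials Office within 24 hours whatever their expectedness, and the annual report in 10.7 covers all new safety information.
- **That the Coordinator may overrule the site on causality.** Section 9.9 describes an independent assessment, states a condition sufficient for SAR status and gives no power to downgrade. Sections 9.2, 9.5 and 9.8 keep the Investigator's role.
- **That Appendix 11, which lists bare reaction names, makes every listed reaction expected even when fatal.** Section 9.7 makes the SmPC the reference for sorafenib and uses Appendix 11 for the embolisation procedure. The SmPC is not part of the protocol, so how far it qualifies reactions by grade or outcome cannot be seen.
- **That the background bleeding rates (under 1% grade 3/4 in both groups of the sorafenib trial in 1.3, 3% gastrointestinal after TACE in 1.2) size the problem.** They count bleeds and say nothing about how often an event would be misclassified.

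It might also be suggested that the SAE form should record causality separately for sorafenib and TACE. The form is not shown, so nothing can be said about what it lacks.

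**Conclusion.** The inconsistency is real and sits at the operative step: one ground of unexpectedness in 9.9 against four in 9.6 and three in 9.3. The consequence is conditional. If 9.9 is followed as written in preference to 9.6, a fatal or unusually severe form of a listed reaction may not be classified as a SUSAR and may miss the 7- or 15-day report under 10.7. Reporting from site to Trials Office is unaffected. On causality, 9.9 leaves out the reporting Investigator and is ambiguous beside 9.5; it does not flatly contradict it.

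The conclusion assumes that the Coordinator works from the text of 9.9 and that some events go beyond the product information in grade, seriousness or outcome but not in nature. The protocol gives no basis for a frequency of such events, so no count is offered. The sponsor's SOP, which is not shown, may already apply the fuller definition. Even so, the protocol should agree with its own definitions.

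**What to change.** In section 9.9:

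1. Replace the nature-only qualifier with: unexpected as defined in section 9.6 (nature, seriousness, severity or outcome).
2. State that an SAE is a SAR if either the reporting Investigator or the Sponsor's assessor (the Chief Investigator or delegated Clinical Coordinator) judges it possibly, probably or definitely related, as in 9.5.

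Both changes restore rules that the protocol already contains. The cost is two sentences of text. The downside is that a few more events may be classified and reported as SUSARs.
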